6.1.6 Definition of On-Treatment

There is no continued study participation for patients who have discontinued treatment early. Consequently off-treatment data capture is expected to be restricted to those data captured during the safety follow-up period specified by the CTP, although there may be occasional unplanned exceptions to this.

Even for patients who completed treatment according to the protocol, data captured during the follow-up period may be relevant for safety.

It is important to be clear whether all available data will be used in a particular summary or analysis, or whether only on-treatment data will be used. The definition of “on-treatment” for this purpose is as described below, and it includes any temporary treatment interruptions which might occur prior to last dose of study treatment. It is assumed that all patients will have a date of last administration of study medication accurately recorded on the End of Treatment eCRF page.

“Off-treatment” refers to data which are captured after baseline but which are not “on-treatment” as defined below.

Safety

An AE start date or other safety assessment date will be considered “on-treatment” if the AE start date or assessment date is between the date of first dose and 28 days after the date of last

dose of study treatment inclusive (the residual effect period (REP) is defined as 28 days in this trial).

The same on-treatment definition will be used for all types of safety data.

Efficacy

All post-baseline efficacy data (including for exploratory biomarkers) will use the same 28-day definition of “on-treatment” as for safety, where on-treatment analyses are specified (as opposed to those efficacy analyses which use all data, both on- and off-treatment).

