7. PLANNED ANALYSIS

Descriptive statistics for continuous variables will generally include N (number of patients with non-missing values), arithmetic mean, standard deviation (SD), minimum, Q1 (lower quartile), median, Q3 (upper quartile) and maximum. In general, means, medians, other quartiles and SDs will be presented to one more decimal place than the raw data. Minimums and maximums will be presented to the same number of decimal places as the raw data.

Tabulations of frequencies for categorical data will include all possible non-missing categories unless otherwise specified, and will display the number of patients in a category as well as the percentage (%) relative to the respective treatment group. Percentages will be rounded to one decimal place. A missing category will be displayed only if there are actually missing values. Percentages will be based on all patients in the respective patient set whether they have non-missing values or not.

Disposition

The disposition of patients will be displayed. This table will present the number of patients enrolled, randomised and treated. The number treated will be further presented separating the dose escalation and maintenance periods. Planned maintenance treatment (see [Section 6.1.2](#)) will be used for this table.

The number of patients who completed or who prematurely discontinued study treatment will be summarised, along with the categorization of the primary reason for treatment discontinuation. The number of patients and reasons for prematurely discontinuing treatment will also be displayed separately for the dose escalation and maintenance periods.

The number of patients who completed or who prematurely withdrew from the study will be summarised, along with the categorization of the primary reason for study withdrawal. It should be noted that in this study, a patient is considered to have completed the study if all scheduled safety follow-up procedures have been performed for that patient, including for patients who discontinued treatment early. In other words, a patient may complete this study without completing treatment.

Where shown on the disposition table, the percentages will be of the number of patients treated in each treatment group.

Kaplan-Meier estimates will be presented graphically by planned maintenance treatment group for time to early treatment discontinuation (defined as *treatment discontinuation date*

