7.8 SAFETY ANALYSIS

All safety analyses will be performed on the TS, including only on-treatment data (unless otherwise specified in [Section 7.8.1](#)). No hypothesis testing is planned for safety.

All specified summaries and analysis will be presented for both actual maintenance treatment and planned maintenance treatment.

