An additional table will present the frequency of patients with AEs by worst CTCAE grade (1 to 5) and by primary SOC and PT. When no events meet the criteria for inclusion, the table will be shown as indicating no events of that type have occurred.

The following tables will be produced separately by baseline body weight subgroup (< 100 / ≥ 100 kg) and by presence of diabetes (yes/no):

- Overall AE summary
- Summary of all AEs by primary SOC and PT
- Summary of AEs leading to treatment discontinuation by primary SOC and PT.

For disclosure of AE data on ClinicalTrials.gov, the frequency of patients with non-serious AEs occurring with an incidence of greater than 5% (PT occurring in more than 5% of treated patients in one or more treatment groups) will be summarised by treatment, primary SOC and PT. The frequency of patients with serious AEs and drug related serious AEs will also be summarised respectively.

For disclosure of AE data in the EudraCT register, the frequency of patients with AEs, the frequency of patients with non-serious AEs with an incidence of greater than 5% (as above) and the frequency of patients with serious AEs will be summarised. Furthermore, the total number of treated patients by country and by age group will be summarised.

An exposure-adjusted summary of all AEs by primary SOC and PT will also be produced. For this purpose, the time at risk will be defined for specific AEs as follows:

- For patients with no events, the time at risk is the number of days on-treatment (inclusive), as defined in [Section 6.1.6](#)
- For patients with one or more event, the time at risk is the number of days from the start of treatment to the start of the first on-treatment event (inclusive).

The total time at risk (years) for a treatment group is the sum of the individual patient times at risk for that treatment group (days) divided by 365.25. Multiple occurrences of the same event for a particular patient will not be counted as separate events in this summary; a patient will either be considered to have no events of the type being summarised, or to have one or more occurrences of that event.

A frequency table will be produced of symptoms of injection site reaction (swelling, induration, heat, redness, pain, other) for the subset of patients with the event.

Additional trial-specific information captured in the eCRF for Grade 3 nausea will be listed only and not summarised.

Adverse Events of Special Interest (AESIs)

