A frequency table will be produced of the following categories. A patient will be included in each relevant category, defined using the maximum post-baseline ALT and AST values observed on-treatment ([Section 6.1.6](#)), regardless of the baseline AST and ALT values:

- ALT or AST ≥ 3 x ULN
- ALT or AST ≥ 5 x ULN
- ALT or AST ≥ 8 x ULN
- ALT or AST ≥ 10 x ULN
- ALT or AST ≥ 20 x ULN
- ALT or AST ≥ 3 x ULN with total bilirubin ≥ 2 x ULN
- ALT or AST ≥ 3 x ULN with INR ≥ 1.5
- ALT or AST ≥ 3 x ULN with either total bilirubin ≥ 2 x ULN or INR ≥ 1.5

In the above categories, each occurrence within a patient of a post-baseline elevation ALT or AST ≥ 3 x ULN will be used as a trigger for the determination of the elevation of total elevation of bilirubin ≥ 2 x ULN or INR ≥ 1.5 , as applicable. The proposed time interval for the follow-up of total bilirubin or INR is 30 days after the occurrence of the post-baseline ALT or AST elevation.

The above frequency table will be repeated using the same categories, but restricted further to patients with a normal baseline value for ALT and AST, defined as both ALT < ULN and AST < ULN.

An additional frequency table will be produced for patients who have an abnormal baseline value for ALT or AST, defined as ALT \geq ULN or AST \geq ULN (or both), and who fall into each of the following categories:

- Both baseline ALT and AST < 2 x ULN and post-baseline ALT or AST > 5 x baseline value
- At least one of baseline ALT or AST ≥ 2 x ULN and < 5 x ULN and post-baseline ALT or AST > 3 x baseline value

- At least one of baseline ALT or AST ≥ 5 x ULN and post-baseline ALT or AST > 2 x baseline value
- Post-baseline ALT or AST > 2 x baseline value with total bilirubin ≥ 2 x ULN or increase in INR > 0.2 .

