7.8.4 ECG

Abnormal findings will be reported as baseline conditions (at screening) or as AEs (during the trial) if judged clinically relevant by the investigator.

The ECG recordings will be centrally evaluated and rated as normal, abnormal, or not evaluable.

All derivations relating to 12-lead ECG variables are given in [Section 5.4.1](#).

Occurrences of values above thresholds will be flagged in the listings. For QTcB and RR, only listings will be provided.

Quantitative variables

Descriptive statistics will be presented over time for absolute values and absolute changes from baseline in the following quantitative ECG variables: QTcF, HR, QT, QRS, PR.

Graphical summaries over time will also be included.

Categorical variables

Frequency tables will be provided for the categorical variables described below, which are determined from the specified quantitative ECG variables:

- New onset (meaning that this or a higher category was not present any time at baseline) of maximum QTcF interval > 450 to 480 msec, > 480 to 500 msec, or > 500 msec on treatment.
- New onset (not present any time at baseline) of uncorrected QT interval > 500 msec at any time on treatment
- Maximum change from baseline of QTcF ≤ 30 msec, > 30 to ≤ 60 msec, or > 60 msec on treatment.
- Maximum change from baseline of QT ≤ 60 msec, or > 60 msec on treatment.

For assignment of a particular patient to one of the above categories, all available time points on-treatment will be considered.

The occurrence of any of the following will be considered as “notable findings” and summarised using frequency tables:

- New onset (not present any time at baseline) of uncorrected QT interval > 500 msec at any time on treatment
- New onset of QTcF interval > 500 msec at any time on treatment
- Change from baseline of QTcF > 60 msec at any time on treatment
- Percentage change from baseline of HR $\geq 25\%$, when corresponding on-treatment value of HR is > 100 beats/min, or percentage change from baseline of HR $\leq -25\%$, when corresponding on-treatment value of HR is < 50 beats/min, at any time on-treatment
- Percentage change from baseline of PR $\geq 25\%$, when corresponding on-treatment value of PR interval is > 200 msec, at any time on treatment
- Percentage change from baseline of QRS $\geq 10\%$, when corresponding on-treatment value of QRS duration is > 110 msec, at any time on treatment.

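### Liver-enzyme, laboratory and ECG threshold tables report only crude ever-on-treatment percentages, which can understate an active-versus-placebo difference if active arms stop early more often

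*SAP*

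**What the plan says.** SAP 7.8 sets the scope: "All safety analyses will be performed on the TS, including only on-treatment data". SAP 7.8.2 places patients in ALT/AST categories "defined using the maximum post-baseline ALT and AST values observed on-treatment", and tabulates the number and percentage with potentially clinically significant laboratory abnormalities. SAP 7.8.4 does the same for new-onset and notable ECG findings: "For assignment of a particular patient to one of the above categories, all available time points on-treatment will be considered".

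The general rule for denominators is in SAP 7: "Percentages will be based on all patients in the respective patient set whether they have non-missing values or not". Some tables are narrower. The ALT/AST table is repeated "restricted further to patients with a normal baseline value for ALT and AST", a further table covers abnormal baselines, and the laboratory-abnormality table shows abnormal baselines separately.

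On follow-up, SAP 6.1.6 says: "There is no continued study participation for patients who have discontinued treatment early". The on-treatment window runs to 28 days after the last dose ("the residual effect period (REP) is defined as 28 days in this trial"). Under the protocol flow chart, a patient who stops has the early-discontinuation visit and one follow-up visit 28 days after it. The follow-up visit has laboratory tests but no ECG.

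For adverse events alone, SAP 7.8.1 adjusts for time at risk: "An exposure-adjusted summary of all AEs by primary SOC and PT will also be produced".

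**The concern.** An ever-crossed percentage depends on how long, and how often, a patient is tested. When a patient stops, testing stops soon afterwards, but the denominator does not shrink. An arm with more early stops therefore has fewer chances to record a crossing.

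The documents give reason to expect unequal stopping between active drug and placebo. Protocol 3.3.4.1 and 4.1.2 lead to discontinuation when intolerance occurs before Visit 14 (Week 12). Protocol 1.2 reports nausea in up to 70% on drug against 23% on placebo in the earlier multiple-dose trial.

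The outcomes matter: hepatic injury is the only pre-specified adverse event of special interest, and conduction and QT effects are named class risks in protocol 1.4.2. At stake is a reader's impression that active drug looks no worse than placebo, or better, on these measures when part of the reason is shorter observation.

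**Working it through.** **Planned figure.** The documents state no discontinuation rate and no crossing rate, so there is no figure of the plan's own to reproduce. Apart from visit counts and arm size, the inputs below are assumptions.

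**Visit counts (flow chart).** Post-baseline laboratory tests and ECGs are scheduled at Weeks 2, 4, 6, 8, 10, 12, 16, 20, 24, 28, 32, 36, 40, 44 and 48, which is 15 visits. A patient stopping at Week 8, 12 or 24 has reached 4, 6 or 9 of them, plus the early-discontinuation visit. The last dose is one week before Visit 32 (protocol 6.2.2), so a completer's follow-up laboratory test falls at about 7 + 28 = 35 days, outside the 28-day window. An early stopper's usually does too.

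**Constant hazard, equal in all arms.** For uncommon crossings the crude ratio is close to the ratio of mean observed weeks. With a share f stopping at week w:

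- Observation ending at the stop: M(f) = f·w + (1 − f)·48.
- Observation to four weeks after the last dose: M(f) = f·(w + 4) + (1 − f)·51, where 51 = 47 + 4.

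For example, with w = 8 and no extra weeks: M(0.1) = 0.8 + 43.2 = 44.0; M(0.4) = 3.2 + 28.8 = 32.0; ratio 32.0/44.0 = 0.73.

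| Stop week, extra weeks | M at 10% | 20% vs 10% | 30% vs 10% | 40% vs 10% |
|---|---|---|---|---|
| 8, none | 44.0 | 0.91 | 0.82 | 0.73 |
| 12, none | 44.4 | 0.92 | 0.84 | 0.76 |
| 8, four | 47.1 | 0.92 | 0.83 | 0.75 |
| 12, four | 47.5 | 0.93 | 0.85 | 0.78 |

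The range is 0.73 to 0.93. ECGs normally end at the early-discontinuation visit, so the rows without extra weeks fit them better.

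**In patients.** Take a 48-week risk of 10%, so cumulative hazard H = −ln(0.9) = 0.1054, and stops at Week 12. A stopper's risk is 1 − exp(−0.1054 × 12/48) = 2.6%. The crude percentage is 0.1 × 2.6 + 0.9 × 10 = 9.3% with 10% stopping, and 0.3 × 2.6 + 0.7 × 10 = 7.8% with 30%. At 60 per arm that is 5.6 against 4.7 expected patients. The rate per patient-year to first event is 11.5 per 100 in both.

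**Front-loaded hazard.** Same 10% risk, equal true hazard, 30% against 10% stopping:

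| Share of hazard placed early | Stop week | Crude ratio | Patient-year rate ratio |
|---|---|---|---|
| 90% in first 12 weeks | 12 | 0.98 | 1.17 |
| 90% in first 24 weeks | 24 | 0.98 | 1.09 |
| 90% in first 24 weeks | 12 | 0.89 | 1.05 |

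First row: a stopper's risk is 1 − exp(−0.9 × 0.1054) = 9.05%. The crude percentages are 0.1 × 9.05 + 0.9 × 10 = 9.90% and 0.3 × 9.05 + 0.7 × 10 = 9.71%, ratio 0.98. Time at risk to first event has ratio 0.84, so the rate ratio is 0.98/0.84 = 1.17. Here the crude percentage is nearly right and the patient-year rate is the misleading one.

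**The case against.** A reader might infer that the percentages are biased by construction. The documents do not support that. A crossing is lost only if it would have come after the stop. Some tabulated crossings are themselves reasons to stop under protocol 3.3.4.1 (QTcF) and 10.1 (ALT/AST), so those patients are counted, and laboratory tests and an ECG follow at the early-discontinuation visit.

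A reader might also infer that hepatic injury gets no exposure adjustment at all. That goes too far. Protocol 5.2.6.1.4 defines the hepatic event of special interest by laboratory criteria and requires it to be reported, and clinically relevant laboratory and ECG changes are recorded as adverse events. These enter the exposure-adjusted table. What remains uncovered is crossings that were neither reported nor judged clinically relevant.

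The passage in protocol 7.5 about tolerability concerns failure to reach the randomised dose, not loss of observation. The first 10 weeks of escalation are identical in all active arms, so early stops support an active-versus-placebo difference, not a gradient across randomised doses.

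Finally, safety is descriptive with no testing. The SAP also plans by-week summaries, exposure tables, Kaplan-Meier discontinuation curves and time profiles for notable ECG findings. These objections limit the size and certainty of the effect. They do not remove it, because none of these displays corrects the threshold percentages for unequal follow-up.

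**Conclusion.** The point holds in a conditional form. The threshold tables have no time-based counterpart, and follow-up depends on time on drug. If active arms stop early more often and crossings continue through treatment, the crude active-to-placebo ratio is pulled down, to about 0.73 to 0.93 when the true ratio is 1. That range rests on an equal constant hazard, stops at Week 8 to 12, and assumed stopping of 20 to 40% against 10%. If most of the hazard falls before the stop, the ratio is about 0.98. If all crossings precede or trigger the stop, there is no bias.

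It is tempting to conclude that arms should be compared on patient-year rates instead. That does not follow: under a front-loaded hazard those rates show 1.05 to 1.17 where there is no true difference, and the documents say nothing about when hepatic or ECG crossings occur. The consequence is limited to how descriptive safety tables are read, so this is a low-cost improvement rather than a flaw in a planned inference.

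**What to change.** In SAP 7.8.2 and 7.8.4, for the ALT/AST categories, the potentially clinically significant laboratory abnormalities and the ECG new-onset and notable findings, keep the crude counts and add:

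- the number of patients per arm with at least one on-treatment post-baseline assessment;
- cumulative incidence to first crossing by arm, censored at the last on-treatment laboratory test or ECG, which needs no constant hazard;
- as a supplement, first occurrences per patient-year by the SAP 7.8.1 method.

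State that arm differences will be read from the crude and time-based displays together, not from the patient-year rate alone. All data are already collected. The cost is slightly longer tables, and censoring at discontinuation must be assumed non-informative. That assumption should be stated, since some crossings lead to the stop.
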